5.2.4.3. Baby (live birth) characteristics and confirmation of birth defects

The baby will be identified using the Mother-Baby link (MBL) available in CPRD **GOLD**. In case of multiple pregnancy, all babies will be followed.

For the live births, the following baby characteristics at birth will be extracted:

- Gender
- Weight
- Length

- Apgar score (at 1 minute and 5 minutes of life)

Codes related to baby's death within 12 weeks of life will be extracted with the associated free text.

Birth defects reported in the mother's file and/or in the baby's files within 12 weeks after delivery will also be extracted with the associated free text.

All cases with an identified birth defect will be reviewed by a GSK Safety physician using the birth defects classification by the CDC Metropolitan Atlanta Congenital Defect Program or MACDP [Centers for Disease Control and Prevention, 2004 and Centers for Disease Control and Prevention, 2007]. Cases with apparent birth defects will be described in detail. Link between medical codes in CPRD *GOLD* and MACDP terminology is detailed in Appendix A.

(Amended 14 March 2013)

5.2.5. Derived variables

5.2.5.1. First day of LMP

Definition of first day of LMP will be as follows:

1. The date of first day of LMP as reported in the database
2. If date of first day of LMP is missing or LMP date is equal to system date (± 2 days) but the EDD is completed in CPRD *GOLD*, the first day of LMP will be calculated as follows: EDD-280 days (*280 days equal to the median of gestational age: 40 weeks*).

(Amended 14 March 2013)

5.2.5.2. First day of gestation

Definition of first day of gestation will be as follows:

1. the day reported as the first day of her LMP,
2. the day adjusted based on available ultrasound scan test data performed at week 12 (± 2 weeks) after first day of LMP. The first day of gestation will be adjusted only if there is a discrepancy between the first day of LMP and the ultrasound-based first day of gestation of seven days or more. Associated free text will be reviewed for the ultrasound scan test performed to adjust for the first day of gestation when needed,
3. if ultrasound scan test data is not available at week 12 (± 2 weeks) after first day of LMP, other ultrasound scan tests will be used to adjust for the first day of gestation knowing that accuracy of gestational age estimation via ultrasound decreases over time as shown in Table 6.

Table 6 Adjustment of the first day of gestation using ultrasound scan test

Ultra-sound completed (Wk)	Ultrasound accuracy (days)	Subject-reported first day of gestation will be adjusted if discrepancy is greater than:
]0-14]	5 - 7	7 days compared to ultrasound-based LMP date
]14-26]	10 - 14	14 days compared to ultrasound-based LMP date
≥ 27	21	21 days compared to ultrasound-based LMP date

All studied pregnancies will be confirmed by the occurrence of at least one other pregnancy identifier between the first day of gestation and the date of end of pregnancy. List of codes (read codes) of pregnancy identifiers are detailed in Appendix A.

Based on the defined first day of gestation, the exposed status (exposed vs. non-exposed) could be adjusted and the subjects will be reassigned to the correct cohort.

5.2.5.3. Time from first day of gestation to spontaneous abortion (UK and US definition)

The primary and first secondary endpoints are the occurrence of spontaneous abortion during the first 23 weeks of gestation (UK definition) and during the first 19 weeks of gestation (US definition). The time (day) from first day of gestation to spontaneous abortion will be computed as the difference between the date of spontaneous abortion and the date of first day of gestation + 1 day.

Time from first day of gestation to spontaneous abortion will be censored at the first of the following events:

- At the end of week 23 (or week 19) for women still pregnant at the beginning of week 24 (or week 20)
- At the time of induced or therapeutic abortion
- At the time of de-enrolment from CPRD *GOLD*, if during the first 23 weeks (or 19 weeks) of gestation
- At the time of death if during the first 23 weeks (or 19 weeks) of pregnancy.

(Amended 14 March 2013)

5.2.5.4. Other derived variables

The following variables will be derived from the CPRD *GOLD* data:

- Woman's date of birth will be defined as the 15th of the birth month and birth year. If the birth month is missing, the birth date will be defined as the 30th June of the birth year
- Incomplete dates will be substituted as follows for calculation of age and/or time to event; if the day is missing the date will be defined as the 15th of the month, if both the day and the month are missing, the date will be defined as 30th June of the year
- Age at first day of gestation will be computed as the difference between the first day of gestation and the date of birth and will be presented in completed year

- Age at a specific event will be computed similarly
- The time from first day of gestation to a specific event (e.g. spontaneous abortion) will be computed as the difference between the date of event (Date1) and the date of first day of gestation (Date0) + 1 and it will be represented in days.

(Amended 14 March 2013)

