5.2.4.2. Pregnancy outcomes

Pregnancy outcomes will be identified using defined algorithms (see Appendix A).

Definition of pregnancy outcomes (according to the UK or US definition):

1. Abortion defined as a loss of pregnancy with the first 23 weeks (≤ 161 days) or within the first 19 weeks (≤ 133 days) of gestation, with the following sub-categories:
 1. Spontaneous abortion
 2. Induced / therapeutic abortion
 3. Other abortion
2. Stillbirth defined as intra-uterine death of foetus after 23 weeks (>161 days) or after 19 weeks (> 133 days) of gestation
3. Live births, with the following sub-categories:
 1. Small for gestational age at birth
 2. Large for gestational age at birth
 3. Pre-term delivery (< 37 weeks of gestation)
 4. Full term delivery (between 37 weeks and 42 completed weeks of gestation)
 5. Post-term delivery (> 42 *completed* weeks of gestation)

(Amended 14 March 2013)

Confirmation of pregnancy outcomes (according to the UK or US definition):

For each pregnancy, the gestational age at outcome will be computed in days as:

- $\text{Gestational_age (days)} = (\text{date of outcome}) - (\text{date of first day of gestation}) + 1$

All abortions and stillbirths will be confirmed using this gestational age:

- if $\text{gestational_age} \leq 161$ days or ≤ 133 days, \rightarrow abortion is confirmed

- if gestational_age > 161 days or > 133 days, → stillbirth is confirmed

For all the identified cases of spontaneous abortion, other abortion, and stillbirth, the associated free text will be reviewed by a GSK-identified reviewer for sub-category classification (spontaneous, induced/therapeutic, and others). As far as possible, other abortion will be re-classified as spontaneous or induced/therapeutic abortion.

Cases of live birth will be classified as pre-term, full term and post-term delivery based on the gestational age at delivery:

- if gestational_age < 259 days then pre-term delivery is confirmed
- if gestational_age \geq 259 and \leq 294 days then full term delivery is confirmed
- if gestational_age > 294 days then post-term delivery is confirmed

Cases of live birth for which confirmation of pre-term, full term or post-term delivery is not possible because the gestational age is missing will be classified as non-confirmed pre-term, full term or post-term delivery, respectively.

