5.6.1. Handling of missing data

Missing data will not be substituted.

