Sheridan A and White J. Annual HPV vaccine coverage in England in 2009/2010. Health Protection Agency Department of Health. Available at: http://www.dh.gov.uk/en/Publicationsandstatistics/Publications/PublicationsPolicyAndGuidance/DH_123795_118052

- **Appendix A, Section 2, Variables derived from CPRD GOLD**

32. First day of LMP:

First day of LMP=EDD-283*

**283 was replaced by 280 during the review of the pregnant women profiles by Pallas to fit the UK definition of the length of pregnancy (40 weeks).*

In Clinical or Referral file where medcode equals to 8879 (=Estimated date of delivery) and First day of LMP=EDD-283*

**283 was replaced by 280 during the review of the pregnant women profiles by Pallas to fit the UK definition of the length of pregnancy (40 weeks)*

33. First day of gestation:

Day of Gestation= EDD-283* OR First Day of Gestation calculated from data_field_2/3 (=estimated size in weeks + Unit). The EDD data field will be also retrieved. **283 was replaced by 280 during the review of the pregnant women profiles by Pallas to fit the UK definition of the length of pregnancy (40 weeks)*

34. Date of delivery: If no information available, the delivery date ~~form~~*from* CPRD GOLD MBL will be used or in *Patient file* mob/yob under baby identifier OR Entity type =115

44. Date of HPV Cervarix vaccination: If at least one dose of Cervarix is between 01Sep2008 and ~~31DEC2010~~ *30JUN2011*, the subject will be included in the eligible population.

- **Appendix B, Table 16 Cox Proportion Hazard analysis of spontaneous abortions: Sensitivity analysis (adjusted for other covariates)**

Other sensitivity analysis ~~with~~ *will* be reported in the same table layout

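### Section 5.2.5.4 fills incomplete outcome dates with the 15th or 30 June while 5.6.1 forbids substitution; 30 June cannot work for early losses, and the 15th can mislabel term class.

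*Combined protocol and SAP*

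**What the plan says.** Section 5.2.5.4 (Other derived variables) gives the filling rule: "Incomplete dates will be substituted as follows for calculation of age and/or time to event". The two cases are "if the day is missing the date will be defined as the 15th of the month" and "if both the day and the month are missing, the date will be defined as 30th June of the year". The same list defines time to a specific event as event date minus first day of gestation plus 1, with spontaneous abortion as its example. The rule therefore reaches the time variable of the primary Cox model (5.2.5.3, 5.6.3.1).

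Section 5.6.1 consists of one sentence: "Missing data will not be substituted". It has no exception for partial dates and does not refer back to 5.2.5.4.

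Section 5.2.4.2 uses the same subtraction: "For each pregnancy, the gestational age at outcome will be computed in days as" date of outcome minus first day of gestation plus 1. It then says "All abortions and stillbirths will be confirmed using this gestational age", with cut-offs at 161 days (UK) and 133 days (US). Live births are split at 259 and 294 days. A live birth that cannot be classed "because the gestational age is missing will be classified as non-confirmed pre-term, full term or post-term delivery". Abortions and stillbirths have no such class.

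Entry (4.2.2.1, 4.2.2.2) requires complete LMP or EDD dates and complete vaccination dates. No such requirement covers outcome dates. Appendix D, listing item 34 of Appendix A, gives the fallback sources for a delivery date when nothing else is available. One of them is the baby's month and year of birth: "mob/yob under baby identifier OR Entity type =115".

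**The concern.** A programmer could follow either section and claim to be following the plan. If 5.2.5.4 is followed, an outcome date that nobody observed is handled as exact to the day and compared with day-level cut-offs.

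Two things are at stake.

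- **Losses.** A filled date can give an impossible time (zero or negative). It can also push a miscarriage past day 161, where it counts as a stillbirth and is censored in the primary analysis. At 11.5% of 243 exposed women about 28 exposed events are expected (0.115 × 243 = 27.9), so each event lost is about 3.6% of them (1/28).
- **Live births.** The non-confirmed class applies only when gestational age is missing. A filled delivery date makes it non-missing, so the birth can be confirmed as pre-term or post-term on an invented day.

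**Working it through.** The plan gives no figure to reproduce here: it does not say how many outcome dates are incomplete. The check applies the 5.2.5.4 rule to each of the 1,033 possible LMP dates from 1 September 2008 to 30 June 2011, with

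T = (outcome date) − (first day of gestation) + 1,

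and compares the class before and after filling. The cut-offs agree with the week definitions: 23 × 7 = 161, 19 × 7 = 133, 37 × 7 = 259, 42 × 7 = 294.

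**Day missing (15th).** The error runs from 15 − 31 = −16 to 15 − 1 = +14 days. A class can change only near a cut-off:

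| Cut-off | True days at which the class can change |
|---|---|
| 161 (UK) | 148 to 177 |
| 133 (US) | 120 to 149 |
| 259 (pre-term) | 245 to 274 |
| 294 (post-term) | 281 to 310 |

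For the UK class, the share of LMP dates misclassified is 0% up to day 147, 23% at day 154, 46% at day 161 and 51% at day 162. Example: LMP 1 July 2009, loss 2 December 2009, T = 155; filled with 15 December, T = 168, a stillbirth. Under the assumed loss distribution given below, fewer than 0.1% of month-only losses change UK class, and none gets a time below 1.

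**Day and month missing (30 June).** The error runs from −184 (true date 31 December) to +180 (1 January; +181 in a leap year). That span is wider than the 161-day window being measured.

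- LMP 10 January 2009, loss 20 March 2009: T = 70 becomes 172.
- LMP 1 September 2009, loss 10 November 2009: T = 71 becomes −62.

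| True day of loss | T of 0 or less | T over 161 |
|---|---|---|
| 42 | 36% | 18% |
| 56 | 31% | 22% |
| 70 | 27% | 26% |
| 84 | 23% | 30% |
| 112 | 15% | 38% |

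The two columns sum to 53% or 54% in every row. The timing assumption changes the split but not the total. Averaged over an assumed loss distribution (28 days plus a gamma variable with shape 3 and scale 13; median about day 63), 28% fall before the first day of gestation and 25% pass day 161.

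**Month-only delivery.** The gestation distribution is not in the documents, so a normal distribution is assumed and varied.

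| Mean, SD (days) | Pre-term: true → after filling | Share of confirmed pre-term that is true |
|---|---|---|
| 280, 10 | 1.6% → 6.0% | 17% |
| 278, 13 | 6.7% → 11.8% | 40% |
| 275, 16 | 15.1% → 19.5% | 59% |

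At mean 278 and SD 13, post-term goes from 10.2% to 13.9%, and about half of those confirmed are true.

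**The case against.** The strongest reply is that this is a wording matter. An incomplete date is not wholly missing, 5.2.5.4 is the specific rule and 5.6.1 the general one, and a cross-reference would settle it. That reading is sensible but unwritten, and it leaves the 30 June rule in force.

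Other parts of the reply stand and limit the point:

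- No passage says outright that a filled date enters the 5.2.4.2 cut-offs. That is inferred from identical arithmetic and the absence of any exclusion. Entry into time to spontaneous abortion, by contrast, is in the text of 5.2.5.4.
- A reader might infer from item 34 that month-only delivery dates are a routine source. They are a fallback for when no other information is available, and they affect secondary endpoints only, because women still pregnant after week 23 are censored at day 161.
- A reader might infer that the primary time-to-event is corrupted. The documents do not show that any loss date is year-only, and month-only losses almost never change UK class.

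Existing checks help in part. Section 5.2.5.2 requires another pregnancy identifier between the first day of gestation and the end of pregnancy. A loss dated before gestation cannot meet that, so it would probably surface. A loss moved past day 161 would not be caught this way. Free text and two blinded experts cover spontaneous and other abortions and stillbirths (5.2.4.2, 5.2.6), and the safety physician sees pre-term and post-term births. None of them is given a rule for an incomplete date.

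**Conclusion.** The point holds as a defect in a stated rule, not as a demonstrated error in the data. Sections 5.2.5.4 and 5.6.1 conflict as written. For any year-only loss, filling with 30 June gives an impossible or out-of-window time about half the time: about 28% before the first day of gestation and 25% past day 161 if the median loss is near day 63. The 15th is harmless for nearly all losses under the primary definition. For month-only deliveries it yields confirmed pre-term births of which about 17% to 59% are truly pre-term, over assumed gestation means of 275 to 280 and SDs of 10 to 16 days.

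All of this is per affected record. The number of such records is unknown and may be small, so the size of any effect on the hazard ratio or odds ratios cannot be stated. The case for changing the plan is that the failure is foreseeable and the repair is mostly wording.

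**What to change.** 1. In 5.2.5.4, drop the 30 June substitution for outcome and event dates. Bound a year-only loss date by the first day of gestation and the woman's other dated pregnancy records, and state which value within the bounds enters the Cox model.
2. Keep the 15th for a month-only loss date, bounded in the same way. Leave the abortion or stillbirth class confirmed unless the possible dates straddle 133 or 161 days. If they do, send the case to the experts of 5.2.6 as undetermined. This class is new, because the non-confirmed class in 5.2.4.2 covers live births only.
3. For live births, use the existing non-confirmed class when the possible dates straddle 259 or 294 days.
4. Make 5.6.1 cross-refer to 5.2.5.4, and report the number of substituted dates per cohort.

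The cost is wording in three sections, one new class and one count. A few losses become undetermined. Most births known only by month become non-confirmed: the full-term window is 294 − 259 + 1 = 36 days, so a 31-day month lies wholly inside it from only 36 − 31 + 1 = 6 starting days. Over the same LMP dates and gestation assumptions, about 80% of month-only births straddle a cut-off. That is few births in total if the fallback is rarely used, and the count in item 4 will show whether it is.

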5.2.6. Final case ascertainment step

*After the first review by the GSK Safety physician (see section 5.2.4.2), individual data related to pregnancy outcomes defined as **spontaneous and other** abortions, stillbirths, **and** baby's death, will be reviewed by two pharmaco-epidemiologists specialised in teratology (see contributors) for final case ascertainment. The experts will be blinded with regards to HPV vaccine exposure. In the event that the experts disagree, a second review step will be conducted and, if they cannot reach an agreement, then the different clinical opinion of the experts will be listed.*

For birth defects (see section 5.2.4.3), when the GSK Safety physician is not able to classify a case, the two experts will be asked to review it and to reach an agreement.

(Amended 14 March 2013)

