Confirmation of cases of “small for gestational age at birth” and of “large for gestational age at birth” will be done as follows by comparing the weight and/or length at birth with the age and sex specific normal weight or length distributions. If the measured weight or length at birth is \leq 10th percentile of normal weight or length, the “small for gestational age at birth” will be confirmed. If the measured weight or length at birth is \geq 90th percentile of normal weight or length, the “large for gestational age at birth” will be confirmed.

Cases of “small for gestational age at birth” and of “large for gestational age at birth” identified in the codes but for which confirmation is not possible because both weight and length at birth are missing will be classified as non-confirmed “small for gestational age at birth” or non-confirmed “large for gestational age at birth”.

The GSK Safety physician will also review the following pregnancy outcomes: abortions (spontaneous abortions, induced/therapeutic abortions, other abortions), stillbirths, neonatal death, for live births: pre-term and post-term delivery, small for gestational age at birth or large for gestational age at birth.

(Amended 14 March 2013)

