5.4. Sample size calculation

Using a two-sided log-rank test with type I error rate of 5% (Software: PASS 2005) and results from the feasibility analysis which has estimated the potential eligible subjects (see section 3.2), the study would have the following power to detect a relative risk (Hazard ratio, HR) of 2.0 of spontaneous abortion between the exposed and non-exposed subjects: 98% power if the first day of LMP is between 30 days before and 45 days after and 99% power if the first day of LMP is between 30 days before and 90 days after any dose of *Cervarix*. The HR detectable with 80% power would be 1.69 and 1.60, respectively.

Those calculations are based on the following assumptions:

- Rate of spontaneous abortion: approximately 11.5% of pregnancies (see section 3.2, feasibility analysis).
- Proportion of dropped out subjects before the first 23 weeks of gestation: 20%.

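### Masking to vaccine exposure is specified only for the final experts, and an abortion moved to induced at an earlier review is censored in the primary analysis without reaching them

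*Combined protocol and SAP*

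**What the plan says.** Outcomes pass through four steps.

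- **Algorithm.** Coded records identify the outcomes (5.2.4.2, Appendix A).
- **Free-text review.** For cases identified as spontaneous abortion, other abortion or stillbirth, a sponsor-identified reviewer (an outside consultancy, 5.2.1) reads the free text and assigns spontaneous, induced/therapeutic or other. Where possible, other abortions are moved to one of the first two categories (5.2.4.2). Masking is not mentioned.
- **Sponsor physician.** "The GSK Safety physician will also review the following pregnancy outcomes: abortions (spontaneous abortions, induced/therapeutic abortions, other abortions), stillbirths, neonatal death" (5.2.4.2). Masking is not mentioned here either. Section 5.2.6 places this review before the experts.
- **Two experts.** They receive spontaneous and other abortions, stillbirths and baby deaths. "The experts will be blinded with regards to HPV vaccine exposure" (5.2.6). If they still disagree after a second review, "then the different clinical opinion of the experts will be listed".

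Sections 5.2.5.3 and 5.5.3.1 censor the primary time-to-event at an induced or therapeutic abortion. Section 5.6.3.1 adds Model 4, which counts spontaneous, induced/therapeutic and other abortions before week 24. Section 5.5.3.1 describes an all-abortions sensitivity analysis whose definition lists induced, therapeutic and other abortions but not spontaneous ones.

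**The concern.** Whether a loss is called spontaneous or induced decides whether it is an event or a censoring in the primary analysis. That call is made, and can be changed, at two steps where the plan is silent on masking. The blinded step that follows corrects errors in one direction only: a case wrongly called spontaneous is seen by the experts, while a case wrongly moved to induced is not. The uncorrected error therefore only takes events out.

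If such moves were unrelated to exposure, they would mainly cost precision. If they were commoner in the exposed cohort, they would pull the hazard ratio down and could hide a risk that this regulator-required safety study exists to detect. If they were commoner in the non-exposed cohort, they would push it up. Stating the masking and closing the route removes the question in either direction.

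**Working it through.** **1. The plan's own figure, as context.** Inputs from 3.2 and 5.4: 243 exposed (−30/+45 days), 667 non-exposed, spontaneous abortion rate 11.5%, HR 2.0, two-sided 5%, dropout 20%. Section 5.4 gives "98% power if the first day of LMP is between 30 days before and 45 days after" and "The HR detectable with 80% power would be 1.69 and 1.60, respectively".

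I used the Freedman log-rank form with unequal allocation: power = Φ(√(D·k)·(HR−1)/(1+k·HR) − 1.96), where k = 243/667 = 0.364.

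- Non-exposed events: 667 × 0.115 = 76.7.
- Exposed events at HR 2.0: 243 × (1 − 0.885²) = 52.7. So D = 129.4.
- Power = Φ(6.87/1.729 − 1.96) = Φ(2.01) = 97.8%. The HR detectable with 80% power is 1.68.

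This matches the plan with no events lost to dropout. With all 20% lost, power is 94.4%. The Schoenfeld form gives 93.7% and 87.7% respectively. The point below does not dispute the stated power.

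**2. What each label does.**

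| Label after the earlier reviews | Goes to blinded experts | Primary Cox model | Model 4 (5.6.3.1) | All abortions as worded in 5.5.3.1 |
|---|---|---|---|---|
| Spontaneous | Yes | Event | Event | Not named |
| Other | Yes | Not an event | Event | Event |
| Induced/therapeutic | No | Censored | Event | Event |

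Only the last row skips the experts. Model 4 is unaffected by a move between rows. Under the 5.5.3.1 wording, a move from spontaneous to induced would add an event to the sensitivity analysis, so that version is not a safeguard.

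**3. Size under no effect (illustration).** Expected exposed events: 243 × 0.115 = 27.9, or × 0.8 = 22.4 after full dropout. Assume that 1, 2 or 3 exposed cases move to induced and the non-exposed cohort is unchanged. The hazard ratio is multiplied by roughly the ratio of event counts.

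- On 27.9: 26.9/27.9 = 0.96, 25.9/27.9 = 0.93, 24.9/27.9 = 0.89. Falls of about 4%, 7% and 11%.
- On 22.4: 21.4/22.4 = 0.96, 20.4/22.4 = 0.91, 19.4/22.4 = 0.87. Falls of about 4%, 9% and 13%.

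**4. Size at the plan's detectable HR of 1.69 (illustration).** Exposed risk = 1 − 0.885^1.69 = 0.187. Exposed events: 45.3, or 36.3 with 20% loss. Non-exposed events: 76.7, or 61.4. After moving m exposed cases, HR = ln(1 − e₁/n₁)/ln(1 − 0.115), with approximate 95% CI HR × exp(±1.96·√(1/e₁ + 1/e₀)).

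- 20% loss (n₁ = 194.4): m = 0 gives 1.69 (1.12–2.55); m = 3 gives 1.54 (1.01–2.34); m = 4 gives 1.49 (0.97–2.28).
- No loss (n₁ = 243): m = 0 gives 1.69 (1.17–2.44); m = 5 gives 1.49 (1.01–2.17); m = 6 gives 1.45 (0.98–2.12).

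So about four to six moved cases, all exposed, would carry the expected lower limit below 1. The number moved is my assumption. The documents give no misclassification rate.

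**5. Unresolved disagreements.** Sections 5.5.3.1 and 5.6.3.1 do not say whether a case with listed opinions is an event or a censoring, and 5.6.1 (missing data are not substituted) does not settle it.

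**The case against.** A reader might infer that an unblinded sponsor physician sorts the abortions. The documents do not support that. They are silent on the physician's masking for abortions, and 5.2.4.2 gives the sub-classification to the free-text reviewer, with the physician reviewing in addition. Appendix D records that the word blinded was removed before the Safety physician, but only for birth-defect review, and it describes superseded text. Section 5.2.6 brings in the experts on birth defects only "when the GSK Safety physician is not able to classify a case"; that does not touch the primary endpoint.

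Knowledge of cohort is also not automatic. Both cohorts are *Cervarix* recipients, so only the interval from dose to LMP separates them. Vaccinations are coded immunisation records, while the requested free text is tied to endpoints. The content of the review profiles, and of Appendix A beyond its amended items, is not shown in the text available, so nothing can be assumed either way.

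The route is narrow. Cases already coded induced are not on the free-text reclassification list; their label comes from routine care. Only an active move to induced escapes blinded review. Model 4 counts the case whichever label it carries. The illustrated shifts are smaller than sampling error: with 27.9 and 76.7 events the 95% CI factor is exp(1.96·√(1/27.9 + 1/76.7)) ≈ 1.54.

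All of this stands, and it limits the point to a gap in safeguards. It does not close the gap: a systematic shift is not made harmless by a wide interval, and Model 4 is a sensitivity analysis with two conflicting definitions. Induced abortions may also dilute its contrast, by an amount that the documents do not allow one to size.

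**Conclusion.** The point holds as a gap in specification and routing. Masking is stated only for the last of the three human reviews, and a case moved to induced before then leaves the primary event count without any blinded check. That error can only remove events. It biases the hazard ratio only if it differs by cohort, and the documents neither show nor exclude this.

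The 4–11% (28 events) and 4–13% (22 events) figures assume that one to three cases move, all exposed and all in one direction. They show sensitivity and predict nothing. A reader might go further and infer that known exposure shapes the primary endpoint; the text does not establish that either earlier reviewer knows exposure.

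The missing rule for unresolved disagreements is, by itself, a matter of missing detail. It belongs here because the choice could otherwise be made with exposure in view. The change is worth making because it is cheap, not because the design fails without it.

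**What to change.** 1. In 5.2.4.2 and 5.2.6, state that the outcome profiles given to the free-text reviewer and the Safety physician omit HPV vaccination records and dates, as for the experts. Appendix D's notes on Appendix A suggest that the review of profiles had begun by Amendment 1. If it was done unmasked, say so and rely on item 2 instead of repeating it. If it was already masked, one sentence settles this item.
2. Send to the blinded experts every abortion whose category was changed at either earlier review, including changes to induced/therapeutic.
3. Before exposure is attached to the adjudicated outcomes, fix how unresolved expert disagreements enter the Cox model, with the opposite assignment as a sensitivity analysis. Which assignment is primary is a convention; what matters is fixing it in advance.
4. Reconcile the all-abortions definition in 5.5.3.1 with Model 4 in 5.6.3.1. It works as a safeguard only if spontaneous abortion is included.

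The cost is a small number of extra cases for the existing experts, and the removal of some fields from the profiles if they are still to be issued. No new data are needed.
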